Colorectal cancer (CRC) survival has improved, but in Scotland, survivors still have notable excess mortality within the first year post diagnosis compared to other European countries. In addition, CRC survivors have high rates of co-morbidities. Evidence suggests that lifestyle improvements have considerable potential to impact on morbidity and recurrence. This study aims to assess the *feasibility* of delivering an intervention programme (TreatWELL) for CRC patients undergoing potentially curative treatments. It is estimated that 30 patients will commence the programme shortly after diagnosis and continue for 31 weeks (to include the period when habits are being re-established). The programme will facilitate stepped changes towards smoking cessation, decreasing alcohol intake, increase in activity to 150 minutes moderate intensity / week and caloric intake appropriate to weight status. Feasibility outcomes include recruitment rates, ease of programme implementation, adherence, patient acceptability or the programme (content, delivery and evaluation measures), factors influencing adherence, retention and delivery costs.

1 INTRODUCTION

1.1 BACKGROUND

Colorectal cancer (CRC) survival has improved in the last decade due to earlier diagnosis and new treatments, but in Scotland, survivors still have notable excess mortality within the first year post diagnosis compared to other European countries¹. Survivors have a high rate of comorbidities including treatment related symptoms which are experienced by 15% undergoing colonic surgery, 33% with rectal surgery, 50% of those with chemo-radiation therapy and 66% of patients undergoing short course radiotherapy. Symptoms include fatigue, physical discomfort and bowel function problems and may be present in 72% of cases². There remains a compelling need to improve outcomes in the early months after diagnosis.

1.2 RATIONALE FOR STUDY

It is recognised that smoking cessation, improved physical activity and diet have potential to impact on treatment outcomes and cancer recurrence.

Physical activity

Observational studies have shown that higher levels of physical activity are associated with better physical functioning³ and reduced fatigue⁴. Follow up studies report better disease free, recurrence free and overall survival^{5,6}. Intervention trials have shown that higher levels of physical activity initiated at pre-habilitation (pre-surgery), post-surgery, during and after adjuvant therapies (re-habilitation)^{7,8,9} are associated with improved cardiorespiratory fitness, muscular strength, physical functioning, quality of life and reduced psychosocial distress.

Diet

There is growing evidence for the impact of diet on CRC outcomes. A large observational study has reported that a western diet resulted in lower disease free and overall survival¹⁰. At intervention level, a trial of dietary counselling delivered during treatment¹¹ showed that nutrition improvements were associated with reduced treatment related co-morbidity at 3 months and after a mean follow up of 6 years. Three post-treatment exploratory trials^{12,13,14} of combined diet and lifestyle interventions have reported improved dietary behaviour, reduced fatigue, improved exercise tolerance, functional capacity and quality of life.

The patient journey

There is some evidence to support lifestyle interventions in the pre-surgery and post treatment periods but no trial has yet evaluated an intervention covering the full patient journey. Patients report confusion about appropriate lifestyle behaviours because they have received differing advice at different treatment stages and rarely receive personalised support in the period after treatments end and during return to normal health¹⁵. It has been noted that only small numbers of CRC patients stop smoking after diagnosis (13.7% pre-diagnosis to 9% 5 months later)¹⁶. Current data suggest that in CRC patients, activity drops significantly by 6 months post-diagnosis¹⁷. This may reflect lack of consistent guidance from clinicians and patient confusion over the merits of rest versus activity¹⁵. Similarly for diet, misconceptions exist over body weight gain (or loss) and understanding appropriate food selection.

Behavioural frameworks and support

There are a number of behavioural frameworks that could support lifestyle change from the start of care, e.g. the concept of the 'teachable moment'¹⁸. Cancer care clinicians can be powerful advocates to help patients understand the importance of lifestyle, from diagnosis throughout the cancer pathway, and have expressed interest in providing guidance¹⁹. Patients consider information obtained from cancer specialists to be of the best quality²⁰. Despite major concerns over their diagnosis, many patients request advice on what might be done to prepare for surgery and there is a need for clinicians to identify an effective programme with the potential to impact on health in the first year after diagnosis. Increasingly, asymptomatic patients picked up on screening mean that this patient group is less frail than those diagnosed late and have considerable potential to initiate lifestyle change. Opportunities in the 'pre-

habilitation' period have been highlighted recently in *Living with and beyond cancer* (2013) but little is known about likely uptake of interventions.

Pilot studies

We have undertaken two pieces of formative work that demonstrate:

- that CRC survivors would welcome guidance on diet in the immediate post-treatment period to alleviate symptoms and fears about food choices: many patients actively seek lifestyle advice but experience confusion, mixed messages, culturally inappropriate guidance and uncertainty about evidence of benefit¹⁵;
- that lifestyle advice by CRC clinicians is restricted due to patient sensitivity, time available, role constraints and lack of skills and resources in this arena¹⁹. These findings suggest that patients are interested in lifestyle but these topics are not routinely addressed by CRC staff.

2 AIMS

This study aims to assess the practical aspects of delivering a lifestyle intervention programme (TreatWELL) for CRC patients undergoing potentially curative treatments in order to inform the feasibility of undertaking a randomised controlled trial (RCT) to evaluate the impact of the intervention programme on health outcomes at one year after diagnosis.

2.1.1 Primary Research Questions

(i) What is the uptake of the proposed intervention programme during the period between diagnosis and surgery?

- What are the recruitment levels that can be achieved within the study duration and how do these vary between disease status and socio-demographic factors?
- How soon after diagnosis can patients commence the intervention programme?

(ii) Can all of the intervention components be delivered in the intervention phases?

- Can the programme be successfully implemented within the NHS setting?
- What is the actual length of time in each phase?
- What is the intervention fidelity to the TreatWELL protocol, which areas present delivery challenges and why?

(iii) What are the responses of patients to the intervention programme and evaluation measures?

- To what extent are patients able to achieve smoking, physical activity and dietary change before, during and after treatment (adherence)?
- Can the proposed evaluation measurements on behavioural and health outcomes (relevant for future RCT) be undertaken successfully?
- What is the retention rate at the end of the study period?

(iv) What are the patients' views on the intervention programme?

- How acceptable are the intervention recruitment methods, programme content, delivery, intensity and exit strategy to participants?
- What factors do patients think influence adherence?

(v) What are the intervention programme delivery costs?

2.2 OUTCOME MEASURES BY RESEARCH QUESTION

Data will be collected at baseline (T0), end of phase 1 (T1, 2 days pre-surgery), end of phase 2 (T2, 3 weeks post-surgery) and end of phase 3 (T3).

2.2.1 Recruitment, retention, socio-demographic and clinical data (RQ i, iii)

The research nurse will prospectively collect details on socio-demographic background, clinical information (including tumour stage and site), type of surgery, stoma status, medications and details of adjuvant treatments. Post-surgical morbidity and hospital stay will

also be recorded. Adverse events (including GP visits and hospital admissions) will be reported at each assessment.

2.2.2 Assessment of ability to undertake evaluation measures and procedures (RQ iii)

Note: these measures will be made to assess whether participants can undertake these procedures (pertinent to the outcomes in a full RCT) but *not* to demonstrate the effect of this feasibility study.

Adherence to intervention will be assessed by

- Self-reported smoking
- Self-reported alcohol intake
- Physical activity by the Scottish physical activity questionnaire (www.dapa-toolkit.mrc.ac.uk/documents/en/SPA/SPAQ.pdf) and the 6 minute walk test.
- Dietary measures by DINE (www.noo.org.uk/uploads/doc/vid_7237_Review_new.pdf)

• Physiological measures (body weight, height, waist circumference, skin fold) Health outcomes

- Fatigue will be measured using the multidimensional fatigue inventory (MFI-20).
- Self-reported bowel function by LARS score²¹.
- Physical function (and role limitations due to physical health) by the EORTC GLQ C30 Quality of Life questionnaire for bowel cancer patients and the EORTC GLQ C29 Quality of Life questionnaire for colorectal cancer patients.

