2.2.3 Time of commencement, NHS implementation and fidelity (RQ i, ii)

The delivery of the intervention programme will be monitored by the lifestyle counsellors who will be asked to complete a structured pro-forma after every patient contact. This will record actual values or scaled ratings on:

- Intervention start time (days after diagnosis)
- Total contact time
- Ease or difficulty of implementing the session
- Perceived fidelity to the intervention programme content and approach
- Extent of patient engagement, receptivity and motivation

Data from pro-formas will be analysed to assess completeness of delivery and areas for improvement, and to provide contextual information (including NHS service issues) on patient engagement.

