All goals are consistent with the American Cancer Society and World Cancer Research Fund guidance for cancer survivors. The behavioural approaches are informed by two main theoretical frameworks: self-regulatory theory and the health action process approach. At each phase of the programme, personalised, specific goals will be identified with a focus on two health behaviours that are selected as a priority for that individual (e.g. smoking, physical activity). All participants will be asked to engage a support person (e.g. spouse) to assist in their adherence with the programme.

Programme content

Smoking

In phase 1 all participants who smoke will be offered a referral to smoking cessation services in the community. Under the national pharmacy contract, public health element, all community pharmacies are commissioned to offer smoking cessation support. In most pharmacies this consists of a brief intervention, one to one support and the provision of free nicotine replacement therapy (NRT) and assessment to meet the needs of the participant. These services will be promoted again as necessary in phases 2 and 3.

Physical activity

In phase 1, participants will be seen for a one hour session where at least 40 minutes will focus on improving cardiovascular fitness prior to surgery. Each participant will be set personalised, ability appropriate physical activity goals aiming towards achieving and/or maintaining 20-25 minutes moderate intensity activity per day (150 minutes per week) plus exercises designed for cardiovascular fitness and muscular strength. If current physical activity is already at that level, participants will be encouraged to maintain this and a modest increase will be encouraged. Participants will be encouraged to develop personalised action and coping plans. Activities (e.g. brisk walking) will be demonstrated and tried by participants and daily goals set. Two telephone calls will be made to participants in the pre-surgery period to enhance compliance and identify and discuss challenges. Personal activity goals will be based on activity levels at baseline measures. Written support material and an exercise DVD will be loaned.

In phase 2, participants will be encouraged to commence activity in accordance with ability, post-op condition and guidance from collaborating physiotherapist.

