In Phase 3, the initial instruction procedure will be repeated and expanded to include emphasis on core strength, mobility and functional ability, with a strict protocol for referral to physiotherapist on any safely issues concerning risk of infection, hernias etc.

Dietary intake and alcohol

In all 3 phases, participants will undergo nutritional screening using the malnutrition universal screening tool (MUST). Participants at risk of malnutrition will be referred to the NHS dietician (as per usual care) for all dietary management. Participants will continue with other aspects of the programme (e.g. smoking cessation and improved physical activity) delivered by the LCs.

In phase 1, advice for participants not at risk of malnutrition (BMI>20kg/m²) will focus on avoiding weight gain and increasing nutrient quality of diet in line with the department of health eatwell model (www.gov.uk/governmenr/uploads/system/uploads/attachment_data/file/ 153475/dh_129974.pdf). Participants will also be advised about decreasing alcohol intake, as appropriate. No energy prescription will be set in phase 1.

In phase 2 and initially in phase 3, nutrition advice will focus on symptom management (e.g. anorexia, vomiting and bowel problems) and work towards achieving a nutrient dense diet. All participants (BMI>20kg/m²) will be given personalised guidance on a nutrient dense diet and avoidance of excess weight gain. Participants with a BMI>25kg/m² will be advised on avoidance of weight gain and modest weight reduction (>5% weight loss) using a personalised energy prescription goal.

Behavioural strategies

Informed by the taxonomy of behaviour change techniques used in interventions and the behaviour change wheel²², a range of evidence-based behavioural techniques will be employed to motivate and support lifestyle change. This will include motivational interviewing, increasing self-efficacy, formation of specific implementation intentions, self-monitoring, personalised action and coping plans, feedback, re-enforcement and social support. To facilitate behaviour change, participants will be offered access to an equipment tool kit (e.g. pedometers, resistance bands and DVDs). Emphasis will be placed on self-monitoring and goal setting, physical activity through pedometers, with weekly feedback in the first week of each phase. In phase 3, the importance of regular self-weighing will be stresses and feedback provided at each telephone consultation.

Programme delivery

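### Adherence is assessed with one list of measures for all participants, but the goals are personal, and the listed data items record neither the priority behaviours, nor the agreed goals, nor whether they were met

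*Protocol*

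**What the plan says.** Research question (iii) in section 2.1.1 is a primary question: "To what extent are patients able to achieve smoking, physical activity and dietary change before, during and after treatment (adherence". Section 8 names adherence as a feasibility measure.

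In section 2.2.2, the line "Adherence to intervention will be assessed by" introduces one list: self-reported smoking and alcohol, the Scottish physical activity questionnaire with the 6 minute walk test, DINE, and weight, height, waist and skinfold. A note at the head of that section gives their purpose: "these measures will be made to assess whether participants can undertake these procedures (pertinent to the outcomes in a full RCT"), and not to show an effect. Section 8 analyses changes between baseline and follow-up and calls the results indicative.

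The intervention in section 3.1 is individual:
- Goals are personal at each phase, "with a focus on two health behaviours that are selected as a priority for that individual".
- For activity, "Each participant will be set personalised, ability appropriate physical activity goals". Those already at the target level are asked to maintain it with a modest increase.
- Cessation referral applies to smokers, and alcohol advice is given where appropriate.
- In phase 1 the weight aim is to avoid gain, without an energy prescription. From phase 2, those with BMI above 25 are also advised to lose more than 5%, while others above 20 are to avoid excess gain.
- Participants at risk of malnutrition pass to the NHS dietician for their diet (also section 6).

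The counsellor pro-forma (sections 2.2.3 and 7.1) records start time, contact time, ease of delivery, "Perceived fidelity to the intervention programme content and approach", and engagement.

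**The concern.** The yardstick does not follow the intervention. A change score on a common instrument shows whether smoking, activity or diet moved. It does not show whether a participant did what was agreed with them. If a behaviour was not a priority for someone, could not apply (a non-smoker), or was managed by the dietician, little change there is not poor adherence to the counsellors' programme.

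A statistical analysis plan could define denominators, but it cannot supply data that were not collected. Which behaviours were prioritised, what goal was set and whether it was met are absent from the items listed for either form.

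Some listed items are also weak indicators of adherence. Height cannot respond to adherence. At T2, three weeks after surgery, walking distance and body measures will largely reflect the operation and recovery. Section 3.1 itself ties phase 2 activity to ability and post-operative condition.

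At stake is whether the study can tell the designers of the future randomised trial how far patients follow the programme as it was agreed with them.

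**Working it through.** **1. The protocol's own figure.** Section 8.1 expects 34 participants, 71% of 48 eligible. 34/48 = 70.8% and 48 × 0.71 = 34.08, so it reproduces. The summary gives 30. The protocol states no adherence figure, threshold or denominator to recompute.

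**2. What can be derived from the listed data** (sections 2.2.1, 2.2.3, 3.3, 7.1).

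| Needed to read adherence against goals | Listed? |
|---|---|
| BMI group | Yes, from weight and height |
| Smoker at baseline | Yes |
| Baseline activity level | Yes, from the questionnaire |
| Behaviours prioritised in each phase | No |
| Goal agreed | No |
| Goal met or not | No |
| Malnutrition screening result or dietician referral | No |

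**3. Possible dilution if all participants are pooled** (illustration). Let s be the share for whom a behaviour is a priority, p1 the attainment among them and p0 the attainment among the rest. Pooled = s × p1 + (1 − s) × p0. If two behaviours are chosen with equal frequency, s = 2/4 for smoking, alcohol, activity and diet, or 2/3 if only three are candidates. The attainment rates are assumed.

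| p1, p0 | s = 1/2 | s = 2/3 | Below p1 by |
|---|---|---|---|
| 60%, 20% | 0.30 + 0.10 = 40% | 0.40 + 0.067 = 47% | 20 or 13 points |
| 60%, 40% | 0.30 + 0.20 = 50% | 0.40 + 0.133 = 53% | 10 or 7 points |
| 50%, 50% | 50% | 50% | 0 |

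**4. Weight.** Suppose everyone with BMI above 25 loses exactly 5% and everyone else stays stable, so that each participant roughly meets the aim. Mean change = −5% × share above 25. For an assumed share of 40% to 80% this is −2.0% to −4.0%. The average understates the loss in the group asked to lose weight.

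**5. Smoking.** Section 1.2 cites 13.7% smoking before diagnosis. If that applied here, 0.137 × 30 = 4.1 and 0.137 × 34 = 4.7, so about 4 to 5 smokers. Counts are all that can usefully be reported.

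**6. Precision after restricting the denominator.** The 95% half-width at 60% is 1.96 × √(0.24/n): 16 points for n = 34 and 23 points for n = 17 (half of 34).

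**The case against.** A reader might infer that each participant works on two behaviours only, so that about half of all participant-behaviour pairs are untargeted and reported adherence is biased downwards by a calculable amount. The protocol does not support this. Two behaviours are a focus and not a limit: every participant receives activity goals, nearly all receive diet guidance, and all smokers are offered referral. A behaviour outside the two priorities is therefore not necessarily untargeted. The protocol also never says that adherence will be pooled. The measures are taken per participant, and denominators may be in an analysis plan that is not shown.

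It is equally tempting to say that the weight aims oppose and cancel each other. They do not. No BMI group named in section 3.1 is asked to gain weight, so averaging dilutes the change. Nor is everything irrecoverable, as the table in the working shows.

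The strongest defence is purpose. Section 2.2.2 says the measures test whether they can be done, section 8 calls changes indicative, and research question (iii) can fairly be read as asking about programme-wide change and not attainment of personal goals. The walk test is also done at T0, T1 and T3, and whether patients can do it at T2 is itself a feasibility question.

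All of this limits the size and consequence of the point. It does not answer the data gap: the same section assigns the list to adherence, and the priorities, goals and attainment are in neither form as listed.

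**Conclusion.** The point holds as a gap in data capture and in the choice of adherence measures. From the listed items, adherence to agreed goals cannot be derived after the study.

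The effect on any reported adherence figure is unknown. In the illustrations it runs from zero (equal attainment) to about 20 percentage points (60% against 20%, two of four behaviours chosen equally often, everyone pooled). Those rates, the equal choice and the pooling are assumptions, so the 20 points is not an estimate of bias.

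No hypothesis test or sample size is affected. The consequence is an answer to research question (iii) that is hard to interpret, with surgical recovery counted as adherence at T2. The change is nearly free if made before the pro-forma is in use, and it should be made.

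**What to change.** 1. Add to the counsellor pro-forma, at each phase: the behaviours prioritised, the goal set, whether it was met, partly met or not met, and whether the participant was referred to the dietician.
2. In section 2.2.2, define adherence per behaviour as goal attainment among those for whom the goal was set, reported alongside the planned changes from baseline.
3. Report weight change by baseline BMI group, identifying those under dietician management, and smoking as counts among baseline smokers.
4. Move the 6 minute walk test and the body measures from the adherence list to health or physical outcomes. They are still collected at the same visits.

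The cost is a few extra fields on a form already completed after every contact, and smaller denominators, hence wider intervals, for each behaviour.

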2.2.3 Time of commencement, NHS implementation and fidelity (RQ i, ii)

The delivery of the intervention programme will be monitored by the lifestyle counsellors who will be asked to complete a structured pro-forma after every patient contact. This will record actual values or scaled ratings on:

- Intervention start time (days after diagnosis)
- Total contact time
- Ease or difficulty of implementing the session
- Perceived fidelity to the intervention programme content and approach
- Extent of patient engagement, receptivity and motivation

Data from pro-formas will be analysed to assess completeness of delivery and areas for improvement, and to provide contextual information (including NHS service issues) on patient engagement.

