8.1 SAMPLE SIZE CALCULATION

This is a feasibility study to test practical aspects of study design which will help inform the calculation of effect sizes required for a subsequent RCT. It is estimated that within the 5 month recruitment period that 60 patients will be diagnosed with CRC and begin treatment. Based on our previous lifestyle trial in CRC patients¹³ it is estimated that 48 of 60 patients will meet the inclusion criteria and 34 (71%) will agree to participate. These numbers should

provide sufficient data on feasibility measures. Feasibility studies are not designed to test hypotheses but to provide data to inform sample size required to show significant differences in health outcome variables in a fully powered RCT.

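### The listed counsellor pro-forma has no record of components planned and delivered, so the component-delivery and fidelity parts of RQ (ii) rest on impressions

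*Protocol*

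**What the plan says.** Section 2.1.1 of the protocol makes delivery a primary research question. RQ (ii) opens with "Can all of the intervention components be delivered in the intervention phases" and adds three sub-questions: "Can the programme be successfully implemented within the NHS setting", "What is the actual length of time in each phase" and "What is the intervention fidelity to the TreatWELL protocol, which areas present delivery challenges and why".

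Section 2.2.3 gives the measurement. Delivery is "monitored by the lifestyle counsellors who will be asked to complete a structured pro-forma after every patient contact". Five items are listed: days from diagnosis to start, contact time, how easy or hard the session was, "Perceived fidelity to the intervention programme content and approach", and the patient's engagement. Section 7.1 lists the same five. Section 2.2.3 then states the use: "Data from pro-formas will be analysed to assess completeness of delivery and areas for improvement". Section 8 repeats that intention and names fidelity to protocol among the feasibility measures.

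Section 2.2.4 adds interviews with the two lifestyle coaches and the research nurse about delivery. It also plans interviews with 10 participants at the end of phase 2 and another 10 at the end of phase 3, with content and delivery among the topics.

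**The concern.** The question is about components, but the listed data are about sessions. No listed item says whether the smoking, activity, diet and alcohol, or behavioural part of the programme was due at a contact, or whether it was given. The one fidelity item combines content with approach and is scored by the counsellors on their own work. A rating of that kind is open to favourable bias, and a low score would not show which component failed or in which phase.

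Section 2 says the study is there to inform an RCT. If a component was often not delivered and the record cannot show it, the RCT could carry that component forward. A weak RCT result would then be hard to separate from non-delivery. The gap also cannot be repaired at analysis: no analysis plan can recover what the form did not capture.

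**Working it through.** No power or error-rate calculation applies: section 8.1 says "Feasibility studies are not designed to test hypotheses", and the point concerns measurement. The check sets each part of RQ (ii) against every delivery data source the protocol lists.

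| Part of RQ (ii) | Listed data that bear on it | Result |
|---|---|---|
| All components delivered, by phase | No pro-forma item; interviews give views only | No record |
| Implementation in the NHS | Session ease or difficulty; contextual service information (2.2.3); staff interviews (2.2.4) | Partly answerable |
| Length of each phase | Start time (2.2.3); surgical and hospital-stay data (2.2.1); timing of T1 to T3 (2.2) | Can be approximated |
| Fidelity | One listed item, self-perceived; no independent check described | Impression only |
| Problem areas and reasons | Session ease or difficulty; staff and participant interviews | Partly answerable |

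**Could another listed item stand in for a component record?** Section 3.1 sets out components that are discrete and checkable. They include a referral offer to smokers, a one-hour phase 1 session with at least 40 minutes on fitness, MUST screening in all three phases, and feedback on self-weighing at phase 3 calls. Total contact time does not show how the hour was divided. A session-level ease rating does not show which component was hard. The time sheets in section 2.2.5 are there for cost.

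**Is there a fixed denominator?** No. Under the theoretical basis in section 3.1, each phase concentrates on two behaviours chosen for the individual. Participants at risk of malnutrition have their dietary management passed to the NHS dietician. What was due therefore differs by person and phase, and without a record of the plan a fidelity score has nothing to be divided by.

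**Planned contacts.** Section 3.1 gives two counts per participant:
- Opening paragraph: 3 face-to-face contacts + at least 12 calls = at least 15.
- Programme delivery: at least 3 visits + 6 to 12 calls, which with 3 visits is 3 + 6 = 9 to 3 + 12 = 15.

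A participant with 3 visits and 6 calls would have 9/9 = 100% of the lower count under the second statement, and 9/15 = 60% of the minimum under the first. This shows only that the denominator is unsettled. It does not measure any shortfall in fidelity.

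**The case against.** The strongest reply is that delivery is not assessed by one rating alone. Contact time, session difficulty and engagement are recorded after every contact, and both those who deliver the programme and some of those who receive it are interviewed. That stands. It rules out two stronger readings that a reader might infer: that a single score decides the matter, and that RQ (ii) cannot be answered at all. The documents do not support either, because implementation, phase length and the reasons for difficulty have data behind them.

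A second reply is that the form itself is not shown. The five entries may be topics with several ratings under each, and item-level form content is often kept outside a protocol. This also stands in part. One cannot say that the form holds no component record, only that the protocol lists none in either place and does not commit to one. As the protocol promises a completeness analysis from this form, the commitment belongs in the text.

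A third reply is that a checklist completed by the counsellors is still self-report. That is true, and it limits what the remedy can claim. Even so, a yes or no against a named component is more specific than a global impression, and it shows where delivery failed.

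The interviews do not close the gap. They collect views, the participant interviews take 10 people at each of two time points, and the staff interviews return largely to the same counsellors.

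**Conclusion.** The point holds in limited form. Of the five listed pro-forma items, one concerns fidelity and none concerns which components were planned or delivered. The headline of RQ (ii), its fidelity sub-question and the completeness analysis promised in sections 2.2.3 and 8 rest on impressions from ratings and interviews. The rest of RQ (ii) is partly answerable as planned.

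The protocol gives no basis for estimating how far self-ratings would overstate delivery, so no figure is offered. The conclusion assumes that the two matching lists describe what the pro-forma will capture. If the form already contains a component record, the remedy shrinks to saying so. In a single-arm feasibility study this is a worthwhile and inexpensive improvement. It does not invalidate the design, but it has to be made before the contacts take place.

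**What to change.** - In sections 2.2.3 and 7.1, add a checklist to the existing pro-forma, completed at each contact. It should give the date and mode of contact; each component planned for that participant in that phase, including the two prioritised behaviours; delivered yes, no or not applicable; and the reason if no.
- State that fidelity will be reported as components delivered divided by components planned, by phase. Keep the perceived rating as context.
- Reconcile the two planned call counts in section 3.1 before reporting contacts delivered against contacts planned. Which count is intended is for the investigators to state.

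The cost is one block on a form already in use, estimated at one to two minutes per contact, with no extra staff and nothing further asked of patients. The downside is slightly more counsellor paperwork. Because the counsellors still complete it, the checklist reduces self-report bias but does not remove it.
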